For the assessment of difference between the gantenerumab group and placebo with regard to the mean change from baseline in each primary endpoint at the end of Week 104, a mixed-effects model repeated measures (MMRM) analysis, incorporating data up to 104 weeks of treatment, was to be used to utilize all the data collected over time. For the primary efficacy analyses, all observations recorded after any modification of the patient's baseline AD medication regimen (change in the dose of the medication or initiation of a new medication) were to be excluded.

For each co-primary endpoint, the model would have included the absolute change from baseline in the endpoint as the dependent variable. The effects in the model would have included independent variables of treatment, assessment weeks relative to the first dose of study drug (i.e., time), treatment-by-time interaction, APOE $\epsilon 4$ status (carrier versus non-carrier), baseline AD medication (either receiving AD treatment or not), and the respective baseline value as covariate. An unstructured variance-covariance structure was to be applied to model the within-patient errors and to enable the inclusion of data from patients with incomplete data across scheduled timepoints.

In order to assess the effect of missing data on the analysis results for the co-primary and key secondary endpoints, sensitivity analyses were to be performed using multiple imputation methods and pattern mixture models. Sensitivity analyses were also to be performed in which observations recorded after any modification of a patient's baseline AD medication regimen would be included.

Additional details will be documented in the Statistical Analysis Plan.

Secondary Analyses

The absolute change from baseline in the continuous secondary efficacy endpoints listed (including cognitive endpoints, global endpoints, disease pathology biomarkers, and endpoints measuring other AD symptoms and effects) was to be analyzed using an MMRM analysis model as described above for the primary efficacy endpoint.

The time to first occurrence of the key secondary endpoint of time to clinical decline was to be analyzed using a stratified proportional hazards model, with APOE $\epsilon 4$ genotype as a stratification factor.

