6.1.3.1 Primary Efficacy Endpoint

The co-primary efficacy endpoints were the absolute change from baseline to the end of Week 104 in ADAS-Cog13 and ADCS-ADL.

For each of the primary endpoints, the null and alternative hypotheses to be tested were:

$$H_0: \mu = 0 \text{ versus } H_A: \mu \neq 0$$

for which μ is the assumed treatment difference in the absolute change from baseline in the endpoint between the gantenerumab and placebo groups. For each endpoint, the null hypothesis of no treatment difference will be rejected if the two-sided p-value is ≤ 0.05 .

The primary efficacy analyses were to include all randomized patients, with patients grouped according to the treatment assigned at randomization.

For the assessment of difference between the gantenerumab group and placebo with regard to the mean change from baseline in each primary endpoint at the end of Week 104, an MMRM analysis, incorporating data up to 104 weeks of treatment, was to be used to utilize all the data collected over time. For the primary efficacy analyses, all observations recorded after any modification of the patient's baseline AD medication

regimen (change in the dose of the medication or initiation of a new medication) were to be excluded.

For each co-primary endpoint, the model would have included the absolute change from baseline in the endpoint as the dependent variable. The effects in the model would have included independent variables of treatment, assessment weeks relative to the first dose of study medication (i.e., time), treatment-by-time interaction, APOE ϵ 4 status (carrier versus non-carrier), baseline AD treatment (either receiving AD treatment or not), and the respective baseline value as a covariate. An unstructured variance-covariance structure was to be applied to model the within-patient errors and to enable the inclusion of data from patients with incomplete data across scheduled timepoints.

In order to assess the effect of missing data on the analysis results for the co-primary and key secondary endpoints, sensitivity analyses were to be performed using multiple imputation methods and pattern mixture models. Sensitivity analyses were also to be performed in which observations recorded after any modification of a patient's baseline AD medication regimen would be included.

Additional details will be documented in the Statistical Analysis Plan.

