1. BACKGROUND

This document describes the statistical data that will be reported in the Clinical Study Report (CSR) for double blind treatment (Part 1) of Study WN28745 and will focus on the statistical methodology underlying the report. The efficacy and safety endpoints that will be the basis for comparing treatments will be defined in full in this document along with the populations of patients that are to be used in the analyses.

Dosing in study WN25203, investigating gantenerumab in prodromal Alzheimer's Disease (AD), was stopped in December 2014 due to a futility analysis. Consequently, recruitment into study WN28745 was stopped early. The final patient was randomized into study WN28745 on the 9th December 2015. Patients active in study WN28745 continued to receive study treatment until they discontinued from the study, finished the study, or transferred into the open label extension (OLE).

Although there will be reporting of study data in a variety of contexts beyond that of the CSR, such as the independent Data Monitoring Committee (iDMC), this document will not cover those contexts.

The description of layouts for the CSR outputs, the details about the underlying analysis datasets and programs, and the linking of production outputs to sections in the CSR are not within the scope of this document and will be covered in separate documents.

The language used in this statistical analysis plan (SAP) supersedes that in the protocol and protocol synopsis.

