2. STUDY DESIGN

WN28745 is a Phase III, multicenter, randomized, double-blind, placebo-controlled, parallel group study to evaluate the safety and efficacy of gantenerumab in patients with mild AD. In part 1 of the study, patients were randomized to receive gantenerumab or placebo in a 1:1 ratio. Patients randomized to gantenerumab received 105mg every 4 weeks (Q4W) for 24 weeks and 225mg from Week 28 to the end of the study provided no amyloid related imaging abnormality-oedema (ARIA-E) and no more than one new amyloid related imaging abnormality-microbleed/hemosiderosis (ARIA-H) were seen on the post Week 24 dose MRI scan. Treatment assignment was stratified by

Apolipoprotein E (*APOE*) genotype (presence or absence of $\epsilon 4$ allele), anti-dementia medications (present or absent) at baseline, and geographic region of the study center (Europe or Rest of World).

The study initially consisted of three phases (Part 1):

1. A screening period of up to 8 weeks.
2. A double-blind treatment period of 100 weeks. A final efficacy and safety assessment to be performed 4 weeks following the patient's last dose (Week 104).
3. A 52 week follow-up period.

The WN28745 protocol was amended in October 2015, following a pre-planned futility analysis in study WN25203, to allow for higher doses of gantenerumab to be studied in Part 2: an OLE. If and when the amended protocol was approved in each country, patients could transition from the main study to the open label extension. This SAP covers data from Part 1 only.

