2.2 ANALYSIS TIMING

The analysis covered in this SAP will include all data from Part 1 for all patients enrolled in study WN28745.

For patients who did not transition into the OLE this will include all data from all visits up to and including the final follow-up visit (Week 152). For patients who transitioned into the OLE, data from all visits up to and including the Week 104/early termination visit (Follow up 1), or last visit prior to first OLE dose, will be included. No data from the OLE will be used. Time windowing will be used to ensure that data from all Week 104/ early termination visits are summarized at the correct time point.

Due to the early transition of this study to an OLE, many patients will not have reached the primary analysis time point as defined in the protocol (Week 104). Consequently, all

analysis results (descriptive and MMRM) will be summarized for Week 48, Week 72 and Week 104.

An interim analysis was originally planned to occur when 50% of patients had completed 104 weeks of double-blind treatment. Due to stopping recruitment into the study and the protocol amendment leading to OLE transition, no such interim analysis will be performed.

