3. STUDY CONDUCT

3.1 RANDOMIZATION ISSUES

To maintain a balanced number of patients enrolled in each treatment arm, randomization was stratified by *APOE* status (presence or absence of $\epsilon 4$ allele) and anti-dementia medications (present or absent) at baseline, and geographic region.

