4.4.1 Primary Efficacy Endpoint

The co-primary efficacy outcome measures are:

- The difference between Gantenerumab and Placebo treated patients in the mean change in ADAS-Cog 13 from baseline (Day 1) to Week 104 in the population of all randomized patients.

- The difference between Gantenerumab and Placebo treated patients in the mean change in ADCS-ADL from baseline (Day 1) to Week 104 in the population of all randomized patients.

For each of the co-primary endpoints, the absolute values, change from baseline and percentage change from baseline will be summarized by time-windowed visit.

In addition, the co-primary endpoints will also be analysed using a mixed model with repeated measures (MMRM). The model will use an unstructured variance – covariance matrix for the repeated measures allowing the inclusion of individuals with incomplete data. The following variables will be included in the modelling:

Dependant variable	ADAS-Cog 13 or ADCS-ADL
Independent variables	Treatment (placebo or Gantenerumab) APOE status (carrier or non-carrier) Baseline ADAS-Cog 13 or ADCS-ADL score Time (weeks relative to first dose in study) Treatment (placebo or Gantenerumab) by time (weeks relative to first dose in study) interaction

Patient, treatment and time will be treated as class variables. All data from all patients (as defined in Section 2.2) will be used, including data from Week 104/early termination visits.

A treatment-by-time interaction contrast will be used to estimate the difference between gantenerumab and placebo in the mean change from baseline at each visit. Least square means, standard errors, 95% confidence intervals will be reported for gantenerumab relative to placebo.

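### The Part 1 SAP's co-primary MMRM adjusts for one of three stratification factors: it drops baseline AD medication without a reason and omits region

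*SAP*

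**What the plan says.** The Part 1 SAP, section 2, lists the stratification factors as APOE ε4 status, "anti-dementia medications (present or absent) at baseline, and geographic region of the study center (Europe or Rest of World". Section 3.1 repeats all three.

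Protocol section 6.1.3.1 defines the co-primary MMRM with treatment, time, their interaction, APOE ε4 status, "baseline AD treatment (either receiving AD treatment or not), and the respective baseline value as a covariate". The protocol synopsis has the same model. Neither includes region.

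Part 1 SAP section 4.4.1 lists treatment, APOE status, baseline score, time and treatment by time. The covariate part of its table reads "status (carrier or non-carrier) Baseline ADAS-Cog 13 or ADCS-ADL score Time (weeks relative to first dose in study". Neither AD medication nor region appears. The model is to yield least-squares means, standard errors and 95% intervals.

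The SAP model governs, because section 1 states: "The language used in this statistical analysis plan (SAP) supersedes that in the protocol and protocol synopsis". Section 2.2 explains the early stop and the added Week 48 and Week 72 summaries. It does not explain the missing medication term.

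**The concern.** A factor used to stratify the allocation is balanced between arms by design. If it also predicts the outcome, that balance makes the treatment estimate less variable. A model without the factor does not see this. It counts the factor's variation as residual error, so the reported standard error exceeds the real sampling variability and the 95% interval covers too often.

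Medication is the clearer case. The sponsor stratified on it and put it in the protocol model. It then disappears from the SAP without comment, and no other model or subgroup analysis in the SAP adjusts for it: section 4.5.8 names only Japan and APOE status.

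Region has a second reason. Section 2 of the Part 1 SAP says: "If and when the amended protocol was approved in each country, patients could transition from the main study to the open label extension". Missing Week 104 data may therefore relate to region, and conditioning on region makes the MMRM's missing-at-random assumption easier to defend.

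**Working it through.** **Planning inputs (protocol 6.1.1).** Differences of 2.3 (SD 10.4) for ADAS-Cog13 and 2.5 (SD 10.9) for ADCS-ADL; 500 per arm; 30% withdrawal; two-sided 0.05. Evaluable per arm: 500 × 0.70 = 350. The standard error is SD × √(2/350), which is 0.786 and 0.824. Power is Φ(2.3/0.786 − 1.96) = 83.3% and Φ(2.5/0.824 − 1.96) = 85.9%. The stated minimum of 80% holds, so these SDs are a usable basis.

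**Actual size.** 389 were randomised (OLE SAP, section 1), or 194.5 per arm. For ADAS-Cog13 with no missing data, SE = 10.4 × √(2/194.5) = 1.055, and the 95% half-width is 1.96 × 1.055 = 2.07.

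**Closed form, one timepoint.** If the omitted factors explain a share R² of the residual variance, the SAP standard error is too wide by 1/√(1 − R²) − 1:

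| R² (assumed) | SE too wide by |
|---|---|
| 0 | 0 |
| 1% | 0.5% |
| 2% | 1.0% |
| 5% | 2.6% |
| 10% | 5.4% |

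A single-visit simulation (N = 389, permuted blocks in 8 strata, 4000 runs) confirms the mechanism at R² = 10%. Without the two factors, the mean model SE is 1.056 against a true SD of 0.985, and the null rejection rate is 3.2%. With them, the figures are 1.002, 0.984 and 4.3%. The true variability hardly changes; the reported standard error does.

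**Repeated measures.** The analysis is longitudinal. For patients who did not enter the OLE, section 2.2 says "this will include all data from all visits up to and including the final follow-up visit (Week 152". Protocol Appendix 1 gives ADAS-Cog13 at Weeks 24, 48, 72, 104, 116 and 152, and ADCS-ADL at Weeks 24, 36, 48, 60, 72, 84, 100, 104, 116 and 152. Of 389 patients, 230 entered the OLE, so 159 (41%) can have Week 116 and 152 data.

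The longitudinal simulation used 250 trials per setting, N = 389, blocks of 4 within strata and an unstructured covariance fitted by REML. Its assumptions are:
- ADAS-Cog13 SD of 5.5, 7.5, 9.0, 10.4, 10.9 and 12.3 at the six visits, multiplied by 10.9/10.4 for ADCS-ADL;
- correlation 0.9 × 0.88^(weeks/26);
- both factors at 50% prevalence.

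In the complete case, all patients are observed to Week 104 and 59% are missing afterwards.

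Week 104 standard errors when each factor's effect grows to 2.3 points:

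| Case | SAP | + medication | + both | + both, by visit | SAP too wide against both (against medication alone) |
|---|---|---|---|---|---|
| ADAS-Cog13, complete | 1.051 | 1.049 | 1.047 | 1.038 | 0.46% (0.25%) |
| ADAS-Cog13, 50% missing | 1.275 | 1.273 | 1.271 | 1.262 | 0.30% (0.17%) |
| ADCS-ADL, complete | 1.106 | 1.104 | 1.103 | 1.094 | 0.32% (0.19%) |
| ADCS-ADL, 50% missing | 1.309 | 1.307 | 1.306 | 1.297 | 0.23% (0.13%) |

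The percentages are means of within-trial ratios, with Monte Carlo error of at most 0.06 points. For ADAS-Cog13 with complete data, 0.46% of a half-width of 1.96 × 1.051 = 2.06 is about 0.01 points.

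Other settings:
- Effects growing to 1 point each: 0.02% to 0.11%.
- Time-constant effects of 2.3 points each, ADAS-Cog13: 1.33% (medication alone 0.68%), or 0.88% (0.47%) with 50% missing.
- Week 104 missingness of 30% against 70% by region, equal in both arms and with no treatment-by-region interaction: 0.29% for ADAS-Cog13 and 0.23% for ADCS-ADL.
- No prognostic effect: adding the two main effects changes the SE by no more than 0.03%.

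**Link between the two methods.** Two 2.3-point effects at 50% prevalence explain 2 × 2.3² × 0.25 = 2.645 of 10.4² = 108.16, so R² = 2.4% and the closed form gives 1.2%. The by-visit model recovers about that much (1.051/1.038). Constant main effects recover 0.46%, because they capture only the part of a growing effect that is common to all visits.

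**The case against.** The strongest reply is that nothing turns on this. Protocol 6.1.7 says the formal primary and key secondary analyses will not be done, and SAP 4.4.1 attaches no decision rule. Even the 2.3-point scenario gives each factor the whole planned ADAS-Cog13 treatment effect, and 50% prevalence maximises the variance explained. All of that stands, and it is why the point is minor.

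Three further arguments stand in part:
- **Medication is not wholly absent from the SAP.** Section 4.3.2 classifies medication ongoing at first dose and provides for summaries, and the baseline list in 4.3.1 is open-ended. AD drugs may therefore be described by arm. Description is not adjustment.
- **Main effects recover only a little over a third of the closed-form loss when effects grow.** That is correct. The closed-form percentages should not be read as the gain from this fix.
- **The ADCS-ADL simulation ignores the rule in 2.3.1.2** that sets total scores to missing for patients from Spain, who fall within the Europe stratum. The absolute standard errors are approximate for that endpoint.

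It can also be said that region is a preference, since the protocol never modelled it. That is fair: adding region is good practice, while the medication term is a real difference between the two documents. None of this supplies a reason for dropping medication.

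**Conclusion.** The point holds and is minor. One of three stratification factors is in the governing model, and a covariate specified in the protocol was removed without explanation.

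With complete data, or missingness unrelated to the factors, leaving out prognostic factors makes the reported standard errors and intervals too wide: 0.02% to 1.33% across the simulated prognostic settings, and nothing if neither factor predicts change. The documents give neither prognostic strength nor prevalence, so they do not show where in that range the trial lies.

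If missing late data depend on region, the effect of omitting region cannot be called conservative in every case. Only one such pattern was simulated, and the documents do not allow any bias to be quantified.

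**What to change.** In Part 1 SAP section 4.4.1, restore baseline anti-dementia medication (present or absent) and add region (Europe or Rest of World) as main effects in both co-primary MMRMs. If medication was removed on purpose, state the reason. If the analysis has already been run, report the adjusted model as a sensitivity analysis.

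The cost is two coefficients per model. Both factors were recorded for randomisation, so no new data are needed.

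Interactions of the two factors with visit are optional. They need 2 × 6 = 12 coefficients for ADAS-Cog13 and 2 × 10 = 20 for ADCS-ADL, so model fit should be checked first. In the simulation they narrowed the Week 104 standard error by 0.8% to 1.3% when both effects grew to 2.3 points, and widened it by up to 0.12% when neither factor mattered.

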4.4.2 Secondary Efficacy Endpoints

The absolute values, change from baseline and percentage change from baseline in the continuous secondary efficacy endpoints listed in Section 2.3.2 will be summarized by time-windowed visit.

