6.1.3.2 Secondary Efficacy Endpoints

The absolute change from baseline in the continuous secondary efficacy endpoints listed in Section 3.5.2 (including cognitive endpoints, global endpoints, disease pathology biomarkers, and endpoints measuring other AD symptoms and effects) was to be analyzed using an MMRM analysis model as described above for the primary efficacy endpoint.

The time to first occurrence of the key secondary endpoint of time to clinical decline was to be analyzed using a stratified proportional hazards model, with APOE ϵ 4 genotype as a stratification factor.

A responder analysis for absolute change from baseline in ADAS-Cog13 at Week 104 was to be performed using a Cochran-Mantel-Haenszel test, with APOE ϵ 4 genotype as a stratification factor. In this analysis, patients who did not have an assessment at Week 104, or who had a modification in the baseline AD medication regimen prior to the Week 104 assessment, were to be considered as non-responders.

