6.1.7 Subgroup Analyses

Since this is a global study, the effect of some demographic variables and baseline characteristic such as race and region on efficacy and safety will be summarized within subgroups using descriptive statistics (please see subgroups below). Additional exploratory analyses of efficacy results may be performed using an MMRM model, with the subgroup, a treatment-by-subgroup interaction term, and a subgroup-by-time interaction terms included along the independent effects described above. This

exploratory subgroup analysis may be important in understanding the effect of these variables on efficacy and safety. Such exploratory analyses will be performed primarily in the case where the descriptive statistics results indicate substantial differences between the subgroups.

The following variables will be used to define the subgroups for these analyses:

- Sex
- Age
- Race
- APOE ϵ 4 status
- Fc γ receptor genotype
- Region

Additional subgroup analyses may be performed with subgroups defined based on baseline levels of CSF t-tau, p-tau, t-tau to A β 1–42 ratio, and p-tau to A β 1–42 ratio.

Since Part 1 (i.e., the double-blind period) has been suspended and replaced by an OLE, the primary and key secondary efficacy analyses will not be performed. However, exploratory and descriptive analyses will be conducted at the end of Part 1.

6.2 ANALYSES IN PART 2

As Part 2 is an OLE, regular safety analyses will be conducted as described in Section 6.1.4. In addition, descriptive statistics and changes from baseline will be used to explore clinical findings (including efficacy, global functioning, and biomarkers). PK analysis will be conducted according to Section 6.1.5.

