1. INTRODUCTION

This document describes the planned statistical analyses that will be reported in the final Clinical Study Report (CSR) for open-label extension (OLE) treatment of Study WN28745. The corresponding protocol version is Version 5.

Study WN28745 was designed as a double-blind, Phase III study (Part I) investigating the effect of 2 years of treatment with subcutaneous (SC) gantenerumab 225 mg versus placebo every 4 weeks (Q4W) on cognition and function in patients with mild Alzheimer's disease (AD). The protocol for this study was amended to an open label extension (OLE) (Part II) to evaluate the safety and tolerability of SC doses of gantenerumab up to 1200 mg Q4W. Enrolment into the double blind (DB) part of the study was halted in December 2015 after 389 patients had been randomized; however, the patients from this study continued dosing while the decision to transition to OLE was made. Enrolment into the WN28745 OLE started on 03 March 2016 and was closed on 31 July 2017; overall, 230 of 389 patients originally randomized into the study entered the OLE part.

The duration of the OLE was up to 5 years. In addition to the initial 2 years in the OLE part, patients were given the option to continue receiving open-label gantenerumab treatment until the end of 2020. Patients who discontinued study drug at any time during the OLE part, or who completed the first 2 years of OLE only were asked to complete follow-up visits at 4 and 16 weeks from their last dose (Follow-Up 1 and 2 respectively)

The description of layouts for the CSR outputs, the details about the underlying analysis datasets and programs, and the linking of production outputs to sections in the final CSR are not within the scope of this document.

The language used in this Statistical Analysis Plan (SAP) supersedes that in the protocol and protocol synopsis.

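### Part 1 secondary efficacy endpoints get observed-case summaries with no between-arm estimate, while the co-primaries keep MMRM: an inconsistent and less efficient choice

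*SAP*

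**What the plan says.** Part 1 SAP 2.3.2 lists four secondary efficacy measures: CDR-GS, CDR-SB, NPI and MMSE. Section 4.4.2 provides that absolute values, change and percentage change "in the continuous secondary efficacy endpoints listed in Section 2.3.2 will be summarized by time-windowed visit". Section 4 defines the descriptive statistics as the number of observations, mean, median, SD, minimum and maximum, with quartiles in selected tables. No model, between-arm difference or confidence interval is specified for these endpoints.

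Section 4.4.1 adds an MMRM for the two co-primaries. Its stated reason for the unstructured covariance is that patients with incomplete data can then be included. Section 4.4 rules out imputation for patients who did not reach Week 104. Section 2.2 says that all "analysis results (descriptive and MMRM) will be summarized for Week 48, Week 72 and Week 104", but does not say which endpoints receive the model.

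Three texts bear on the comparison with the protocol:
- Protocol 6.1.3.2 had planned for the continuous secondary endpoints to be "analyzed using an MMRM analysis model as described above for the primary efficacy" endpoint.
- Protocol 6.1.7 then states that, because Part 1 was suspended, "the primary and key secondary efficacy analyses will not be performed", and that "exploratory and descriptive analyses will be conducted at the end of Part 1".
- Part 1 SAP Section 1 states: "The language used in this statistical analysis plan (SAP) supersedes that in the protocol and protocol synopsis".

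On the extent of loss, Part 1 SAP 2.2 says only that many patients will not have reached Week 104. The introduction to the open-label extension (OLE) SAP adds that "overall, 230 of 389 patients originally randomized into the study entered the OLE part".

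**The concern.** The reason for keeping MMRM on the co-primaries, namely that many patients have incomplete follow-up, applies equally to the secondaries. Protocol Appendix 1 schedules CDR and NPI at the same post-baseline treatment visits as ADAS-Cog13 (Weeks 24, 48, 72 and 104) and MMSE more often, so the data the model needs are already collected.

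Three things are at stake. First, Section 4.4 offers the by-visit summaries as a way to compare the arms, yet for the secondaries no statistic makes that comparison. Second, a Week 72 or Week 104 observed-case mean uses only patients assessed in that window, so the earlier course of those who left adds nothing and precision is lost. Third, an observed-case mean is unbiased only if leaving is unrelated to outcome, whereas a likelihood-based model needs only the weaker missing-at-random assumption.

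**Working it through.** **1. The plan's own figure.** The documents give no sample size, power or standard error for the secondary endpoints. The only sample-size claim is at least 80% power for each co-primary with 500 per arm and 30% withdrawal (Protocol 6.1.1). Evaluable patients are 500 × 0.7 = 350 per arm, and power is Φ(δ/SD ÷ √(2/350) − 1.96):
- ADAS-Cog13: 2.3/10.4 = 0.221; 0.221/0.0756 = 2.926; power 83.3%.
- ADCS-ADL: 2.5/10.9 = 0.229; 0.229/0.0756 = 3.034; power 85.9%.

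The claim reproduces. It says nothing about the secondaries.

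**2. Which text governs.** CDR-SB is a key secondary (Protocol 3.5.2), so Protocol 6.1.7 withdraws its planned analysis. CDR-GS, MMSE and NPI are additional secondaries and that sentence does not name them. The same sentence withdraws the primary analyses, yet the SAP retains a model for those.

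**3. How many left, and when.** OLE entrants: 230/389 = 59.1%, leaving 159 (40.9%). This counts entry at any time. The last patient was randomized on 9 December 2015 (Part 1 SAP Section 1). OLE enrolment ran from 3 March 2016 to 31 July 2017 (OLE SAP Section 1), which is 85/7 = 12.1 to 600/7 = 85.7 weeks later. The latest-randomized entrants could not have reached Week 104 first; earlier-randomized ones could. The number lost before Week 72 or 104 cannot be derived.

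**4. Precision.** The documents give neither retention by visit nor within-patient correlation, so both are assumptions: three retention patterns, and ρ of 0.5, 0.65 and 0.8 with AR(1) and compound-symmetric structures. With 389 patients split 1:1 and outcome SD 1, the observed-case SE of the between-arm difference at retention r is √(4/(389r)). At r = 0.40 this is √(4/155.6) = 0.160. The MMRM SE comes from the inverse of the summed information over monotone dropout patterns at Weeks 24, 48, 72 and 104. A hand check with one earlier visit seen in everyone is SE ratio = √(1 − ρ²(1 − r)); for ρ = 0.7 and r = 0.41 it is √(1 − 0.49 × 0.59) = 0.843.

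| Retention at Weeks 24/48/72/104 | Visit | Observed-case SE (SD units) | MMRM SE ÷ observed-case SE | Observed-case SE larger by |
|---|---|---|---|---|
| 100/85/60/40% | 72 | 0.131 | 0.850–0.959 | 4–18% |
| | 104 | 0.160 | 0.754–0.950 | 5–33% |
| 100/80/50/25% | 72 | 0.143 | 0.808–0.948 | 5–24% |
| | 104 | 0.203 | 0.676–0.929 | 8–48% |
| 95/80/65/50% | 72 | 0.126 | 0.886–0.972 | 3–13% |
| | 104 | 0.143 | 0.815–0.965 | 4–23% |

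The extremes are 1/0.965 = 1.04 and 1/0.676 = 1.48 at Week 104, and 1/0.972 = 1.03 and 1/0.808 = 1.24 at Week 72.

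**5. Bias.** This was simulated with one earlier and one late visit, correlation 0.5 to 0.8 and late retention 25% to 60%. If leaving is administrative, the observed-case arm mean has no bias. If the odds of leaving rise 1.5- to 2-fold per SD of worse earlier change, the arm mean understates decline by 0.08 to 0.39 SD; the likelihood-based estimate has essentially none.

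The between-arm difference is far less affected when the mechanism is the same in both arms. This can be illustrated on the ADAS-Cog13 planning figures (placebo decline 10, SD 10.4, difference 2.3), since none are given for the secondaries. With about 36% retained, the placebo decline fell to about 8.4–8.7, but the difference moved only to about 2.2, or (2.3 − 2.2)/2.3 ≈ 4%.

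**The case against.** The best defence is that descriptive summaries are what the current protocol provides. Protocol 6.1.7 replaces the key secondary analyses, including CDR-SB, with exploratory and descriptive ones, and the SAP overrides the protocol in any case. Protocol 1.4.1.2 regards the Part 1 doses as subtherapeutic, so no confirmatory decision rests on these endpoints. The tables give N, mean and SD, from which a crude difference and interval can be calculated. All of this stands, and it limits the point to an improvement. It does not explain why the co-primaries, withdrawn by the same sentence, keep a model. Nor does an exploratory MMRM conflict with Protocol 6.1.7.

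A reader might infer three stronger things that the documents do not support:
- *That the SAP breaches the protocol.* For CDR-SB the planned analysis was expressly withdrawn. For MMSE, NPI and CDR-GS a departure is arguable, but the precedence clause settles which text governs.
- *That data from patients who moved to the OLE are thrown away.* Section 2.2 includes their Part 1 visits, and Section 4.4 places early-termination data in the window where they were collected. Those data are reported; they just do not inform later visits.
- *That most patients were lost before the late visits and the results are therefore biased.* The 59.1% is entry at any time, and Section 2.2 allows for entrants with a Week 104 visit. Transfer followed country approval of the amendment (Part 1 SAP Section 2), which is largely administrative.

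Outcome-related loss remains possible. Protocol 4.3.2.3 required discontinuation from the study for changes in AD medication in the first 6 months, plausibly linked to decline. Equal mechanisms in the two arms are not assured: adverse-event withdrawal in Study WN25203 was 5.3% on placebo and 9.6% on 225 mg (Protocol 1.3.3). These facts show a risk, not its size in this trial.

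**Conclusion.** The point holds as an inconsistent and less efficient analysis choice, not as an error or a clear protocol departure. The plainest gap is that no between-arm estimate or interval is planned for any secondary efficacy endpoint. The precision ranges in the table (4% to 48% at Week 104, 3% to 24% at Week 72) rest wholly on the assumed correlations and retention, but some loss occurs even if every exit was administrative. Bias in arm means is conditional on leaving being related to earlier decline. Bias in the treatment difference should be small unless the arms lost patients for different reasons. MMRM is valid under missing at random and does not protect against loss that depends on unobserved outcomes.

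**What to change.** In Part 1 SAP 4.4.2, apply the Section 4.4.1 MMRM to CDR-SB, MMSE and NPI total, with the same covariates and each endpoint's own baseline. State whether NPI total means the 10- or 12-item score. Name the population as all randomized patients by randomized arm: Section 4.4.1 uses all randomized patients, but Section 4.1.2 calls the safety population primary for these outcomes, so the choice must be explicit. Report least-squares mean differences with 95% confidence intervals at Weeks 48, 72 and 104, labelled exploratory. Leave CDR-GS descriptive, because it is an ordinal score. Keep the descriptive tables and add, by arm, the number observed at each visit and the reasons for leaving (OLE transfer separately from other causes).

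The cost is SAP wording and running an already specified model on three more endpoints; no new data are needed. The downside is a little more analysis work and some additional non-confirmatory estimates that must not be read as tests.
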